**ATTACHMENT 4: TEMOZOLOMIDE PRESCRIBING INFORMATION**

## HIGHLIGHTS OF PRESCRIBING INFORMATION

These highlights do not include all the information needed to use TEMODAR safely and effectively. See full prescribing information for TEMODAR.

TEMODAR® (temozolomide) Capsules  
TEMODAR® (temozolomide) for Injection  
administered via intravenous infusion  
Initial U.S. Approval: 1999

### INDICATIONS AND USAGE

TEMODAR is an alkylating drug indicated for the treatment of adult patients with:

- Newly diagnosed glioblastoma multiforme (GBM) concomitantly with radiotherapy and then as maintenance treatment. (1.1)
- Refractory anaplastic astrocytoma patients who have experienced disease progression on a drug regimen containing nitrosourea and procarbazine. (1.2)

### DOSAGE AND ADMINISTRATION

- Newly Diagnosed GBM: 75 mg/m^2 for 42 days concomitant with focal radiotherapy followed by initial maintenance dose of 150 mg/m^2 once daily for Days 1-5 of a 28-day cycle of TEMODAR for 6 cycles. (2.1)
- Refractory Anaplastic Astrocytoma: Initial dose 150 mg/m^2 once daily for 5 consecutive days per 28-day treatment cycle. (2.1)
- The recommended dose for TEMODAR as an intravenous infusion over 90 minutes is the same as the dose for the oral capsule formulation. Bioequivalence has been established only when TEMODAR for Injection was given over 90 minutes. (2.1, 12.3)

### DOSAGE FORMS AND STRENGTHS

- 5-mg, 20-mg, 100-mg, 140-mg, 180-mg, and 250-mg capsules. (3)
- 100-mg powder for injection. (3)

### CONTRAINDICATIONS

- Known hypersensitivity to any TEMODAR component or to dacarbazine (DTIC). (4.1)

### WARNINGS AND PRECAUTIONS

- Myelosuppression — monitor Absolute Neutrophil Count (ANC) and platelet count prior to dosing and throughout treatment. Geriatric patients and women have a higher risk of developing myelosuppression. (5.1)
- Cases of myelodysplastic syndrome and secondary malignancies, including myeloid leukemia, have been observed. (5.2)

- Pneumocystis carinii* pneumonia (PCP) – prophylaxis required for all patients receiving concomitant TEMODAR and radiotherapy for the 42-day regimen for the treatment of newly diagnosed glioblastoma multiforme. (5.3)
- All patients, particularly those receiving steroids, should be observed closely for the development of lymphopenia and PCP. (5.4)
- Complete blood counts should be obtained throughout the treatment course as specified. (5.4)
- Fetal harm can occur when administered to a pregnant woman. Women should be advised to avoid becoming pregnant when receiving TEMODAR. (5.5)
- As bioequivalence has been established only when given over 90 minutes, infusion over a shorter or longer period of time may result in suboptimal dosing; the possibility of an increase in infusion-related adverse reactions cannot be ruled out. (5.6)

### ADVERSE REACTIONS

- The most common adverse reactions (≥10% incidence) are: alopecia, fatigue, nausea, vomiting, headache, constipation, anorexia, convulsions, rash, hemiparesis, diarrhea, asthenia, fever, dizziness, coordination abnormal, viral infection, amnesia, and insomnia. (6.1)
- The most common Grade 3 to 4 hematologic laboratory abnormalities (≥10% incidence) that have developed during treatment with temozolomide are: lymphopenia, thrombocytopenia, neutropenia, and leukopenia. (6.1)
- Allergic reactions have also been reported. (6)

To report SUSPECTED ADVERSE REACTIONS, contact Merck Sharp & Dohme Corp., a subsidiary of Merck & Co., Inc., at [name] or FDA at [name] or [www.fda.gov/medwatch](http://www.fda.gov/medwatch).

### DRUG INTERACTIONS

- Valproic acid: decreases oral clearance of temozolomide. (7.1)

### USE IN SPECIFIC POPULATIONS

- Nursing mothers: Not recommended. (8.3)
- Pediatric use: No established use. (8.4)
- Hepatic/Renal Impairment: Caution should be exercised when TEMODAR is administered to patients with severe renal or hepatic impairment. (8.6, 8.7)

See 17 for PATIENT COUNSELING INFORMATION and FDA-approved patient labeling.

Revised: 06/2013

## FULL PRESCRIBING INFORMATION

### 1 INDICATIONS AND USAGE

#### 1.1 Newly Diagnosed Glioblastoma Multiforme

TEMODAR® (temozolomide) is indicated for the treatment of adult patients with newly diagnosed glioblastoma multiforme concomitantly with radiotherapy and then as maintenance treatment.

#### 1.2 Refractory Anaplastic Astrocytoma

TEMODAR is indicated for the treatment of adult patients with refractory anaplastic astrocytoma, i.e., patients who have experienced disease progression on a drug regimen containing nitrosourea and procarbazine.

### 2 DOSAGE AND ADMINISTRATION

#### 2.1 Recommended Dosing and Dose Modification Guidelines

The recommended dose for TEMODAR as an intravenous infusion over 90 minutes is the same as the dose for the oral capsule formulation. Bioequivalence has been established only when TEMODAR for Injection was given over 90 minutes [see *Clinical Pharmacology* (12.3)]. Dosage of TEMODAR must be adjusted according to nadir neutrophil and platelet counts in the previous cycle and the neutrophil and platelet counts at the time of initiating the next cycle. For TEMODAR dosage calculations based on body surface area (BSA) see **Table 5**. For suggested capsule combinations on a daily dose see **Table 6**.

**Patients with Newly Diagnosed High Grade Glioma: Concomitant Phase:** TEMODAR is administered at 75 mg/m^2 daily for 42 days concomitant with focal radiotherapy (60 Gy administered in 30 fractions) followed by maintenance TEMODAR for 6 cycles. Focal RT includes the tumor bed or resection site with a 2- to 3-cm margin. No dose reductions are recommended during the concomitant phase; however, dose interruptions or discontinuation may occur based on toxicity. The TEMODAR dose should be continued throughout the 42-day concomitant period up to 49 days if all of the following conditions are met: absolute neutrophil count greater than or equal to 1.5 x 10^9/L, platelet count greater than or equal to 100 x 10^9/L, common toxicity criteria (CTC) nonhematological toxicity less than or equal to Grade 1 (except for alopecia, nausea, and vomiting). During treatment a complete blood count should be obtained weekly. Temozolomide dosing should be interrupted or discontinued during concomitant phase according to the hematological and nonhematological toxicity criteria as noted in **Table 1**. *Pneumocystis carinii* pneumonia (PCP) prophylaxis is required during the concomitant administration of TEMODAR and radiotherapy, and should be continued in patients who develop lymphocytopenia until recovery from lymphocytopenia (CTC Grade less than or equal to 1).

**TABLE 1: Temozolomide Dosing Interruption or Discontinuation During Concomitant Radiotherapy and Temozolomide**

Toxicity	TMZ Interruption*	TMZ Discontinuation
Absolute Neutrophil Count	greater than or equal to 0.5 and less than 1.5 x 10  /L	less than 0.5 x 10  /L
Platelet Count	greater than or equal to 10 and less than 100 x 10  /L	less than 10 x 10  /L
CTC Nonhematological Toxicity (except for alopecia, nausea, vomiting)	CTC Grade 2	CTC Grade 3 or 4

\*Treatment with concomitant TMZ could be continued when all of the following conditions were met: absolute neutrophil count greater than or equal to 1.5 x 10^9/L; platelet count greater than or equal to 100 x 10^9/L; CTC nonhematological toxicity less than or equal to Grade 1 (except for alopecia, nausea, vomiting). TMZ=temozolomide; CTC=Common Toxicity Criteria.

#### Maintenance Phase:

**Cycle 1:** Four weeks after completing the TEMODAR+RT phase, TEMODAR is administered for an additional 6 cycles of maintenance treatment. Dosage in Cycle 1 (maintenance) is 150 mg/m^2 once daily for 5 days followed by 23 days without treatment.

**Cycles 2-6:** At the start of Cycle 2, the dose can be escalated to 200 mg/m^2, if the CTC nonhematologic toxicity for Cycle 1 is Grade less than or equal to 2 (except for alopecia, nausea, and vomiting), absolute neutrophil count (ANC) is greater than or equal to 1.5 x 10^9/L, and the platelet count is greater than or equal to 100 x 10^9/L. The dose remains at 200 mg/m^2 per day for the first 5 days of each subsequent cycle except if toxicity occurs. If the dose was not escalated at Cycle 2, escalation should not be done in subsequent cycles.

**Dose Reduction or Discontinuation During Maintenance:** Dose reductions during the maintenance phase should be applied according to **Tables 2** and **3**.

During treatment, a complete blood count should be obtained on Day 22 (21 days after the first dose of TEMODAR) or within 48 hours of that day, and weekly until the ANC is above 1.5 x 10^9/L (1500/μL) and the platelet count exceeds 100 x 10^9/L (100,000/μL). The next cycle of TEMODAR should not be started until the ANC and platelet count exceed these levels. Dose reductions during the next cycle should be based on the lowest blood counts and worst nonhematologic toxicity during the previous cycle. Dose reductions or discontinuations during the maintenance phase should be applied according to **Tables 2** and **3**.

**TABLE 2: Temozolomide Dose Levels for Maintenance Treatment**

Dose Level	Dose (mg/m  /day)	Remarks
-1	100	Reduction for prior toxicity
0	150	Dose during Cycle 1
1	200	Dose during Cycles 2-6 in absence of toxicity

**TABLE 3: Temozolomide Dose Reduction or Discontinuation During Maintenance Treatment**

Toxicity	Reduce TMZ by 1 Dose Level*	Discontinue TMZ
Absolute Neutrophil Count	less than $1.0 \times 10^9/L$	See footnote†
Platelet Count	less than $50 \times 10^9/L$	See footnote†
CTC Nonhematological Toxicity (except for alopecia, nausea, vomiting)	CTC Grade 3	CTC Grade 4†

[figure not shown]
\*TMZ dose levels are listed in Table 2.

†TMZ is to be discontinued if dose reduction to less than 100 mg/m^2 is required or if the same Grade 3 nonhematological toxicity (except for alopecia, nausea, vomiting) recurs after dose reduction.

TMZ=temozolomide; CTC=Common Toxicity Criteria.

**Patients with Refractory Anaplastic Astrocytoma:** For adults the initial dose is 150 mg/m^2 once daily for 5 consecutive days per 28-day treatment cycle. For adult patients, if both the nadir and day of dosing (Day 29, Day 1 of next cycle) ANC are greater than or equal to  $1.5 \times 10^9/L$  (1500/ $\mu$ L) and both the nadir and Day 29, Day 1 of next cycle platelet counts are greater than or equal to  $100 \times 10^9/L$  (100,000/ $\mu$ L), the TEMODAR dose may be increased to 200 mg/m^2/day for 5 consecutive days per 28-day treatment cycle. During treatment, a complete blood count should be obtained on Day 22 (21 days after the first dose) or within 48 hours of that day, and weekly until the ANC is above  $1.5 \times 10^9/L$  (1500/ $\mu$ L) and the platelet count exceeds  $100 \times 10^9/L$  (100,000/ $\mu$ L). The next cycle of TEMODAR should not be started until the ANC and platelet count exceed these levels. If the ANC falls to less than  $1.0 \times 10^9/L$  (1000/ $\mu$ L) or the platelet count is less than  $50 \times 10^9/L$  (50,000/ $\mu$ L) during any cycle, the next cycle should be reduced by 50 mg/m^2, but not below 100 mg/m^2, the lowest recommended dose (see Table 4). TEMODAR therapy can be continued until disease progression. In the clinical trial, treatment could be continued for a maximum of 2 years, but the optimum duration of therapy is not known.

**TABLE 4: Dosing Modification Table**

**TABLE 5: Daily Dose Calculations by Body Surface Area (BSA)**

Total BSA (m  )	75 mg/m  (mg daily)	150 mg/m  (mg daily)	200 mg/m  (mg daily)
1.0	75	150	200
1.1	82.5	165	220
1.2	90	180	240
1.3	97.5	195	260
1.4	105	210	280
1.5	112.5	225	300
1.6	120	240	320
1.7	127.5	255	340
1.8	135	270	360
1.9	142.5	285	380
2.0	150	300	400
2.1	157.5	315	420
2.2	165	330	440
2.3	172.5	345	460
2.4	180	360	480
2.5	187.5	375	500

**TABLE 6: Suggested Capsule Combinations Based on Daily Dose in Adults**

Total Daily Dose (mg)	Number of Daily Capsules by Strength (mg)					
	250 mg	180 mg	140 mg	100 mg	20 mg	5 mg
75	0	0	0	0	3	3
82.5	0	0	0	0	4	0
90	0	0	0	0	4	2
97.5	0	0	0	1	0	0
105	0	0	0	1	0	1
112.5	0	0	0	1	0	2
120	0	0	0	1	1	0
127.5	0	0	0	1	1	1
135	0	0	0	1	1	3
142.5	0	0	1	0	0	0
150	0	0	1	0	0	2
157.5	0	0	1	0	1	0
165	0	0	1	0	1	1
172.5	0	0	1	0	1	2
180	0	1	0	0	0	0
187.5	0	1	0	0	0	1
195	0	1	0	0	0	3
200	0	1	0	0	1	0
210	0	0	0	2	0	2
220	0	0	0	2	1	0
225	0	0	0	2	1	1
240	0	0	1	1	0	0
255	1	0	0	0	0	1
260	1	0	0	0	0	2
270	1	0	0	0	1	0
280	0	0	2	0	0	0
285	0	0	2	0	0	1
300	0	0	0	3	0	0
315	0	0	0	3	0	3
320	0	1	1	0	0	0
330	0	1	1	0	0	2
340	0	1	1	0	1	0
345	0	1	1	0	1	1
360	0	2	0	0	0	0
375	0	2	0	0	0	3
380	0	1	0	2	0	0
400	0	0	0	4	0	0
420	0	0	3	0	0	0
440	0	0	3	0	1	0
460	0	2	0	1	0	0
480	0	1	0	3	0	0
500	2	0	0	0	0	0

**2.2 Preparation and Administration**

**TEMODAR Capsules:** In clinical trials, TEMODAR was administered under both fasting and nonfasting conditions; however, absorption is affected by food [see *Clinical Pharmacology* (12.3)], and consistency of administration with respect to food is recommended. There are no dietary restrictions with TEMODAR. To reduce nausea and vomiting, TEMODAR should be taken on an empty stomach. Bedtime administration may be advised. Antiemetic therapy may be administered prior to and/or following administration of TEMODAR.

TEMODAR (temozolomide) Capsules should not be opened or chewed. They should be swallowed whole with a glass of water.

If capsules are accidentally opened or damaged, precautions should be taken to avoid inhalation or contact with the skin or mucous membranes [see *How Supplied/Storage and Handling* (16.1)].

**TEMODAR for Injection:** Each vial of TEMODAR for Injection contains sterile and pyrogen-free temozolomide lyophilized powder. When reconstituted with 41 mL Sterile Water for Injection, the resulting solution will contain 2.5 mg/mL temozolomide. Bring the vial to room temperature prior to reconstitution with Sterile Water for Injection. The vials should be gently swirled and not shaken. Vials should be inspected, and any vial containing visible particulate matter should not be used. Do not further dilute the reconstituted solution. After reconstitution, store at room temperature (25°C [77°F]). Reconstituted product must be used within 14 hours, including infusion time.

Using aseptic technique, withdraw up to 40 mL from each vial to make up the total dose based on **Table 5** above and transfer into an empty 250 mL infusion bag (2). TEMODAR for Injection should be infused intravenously using a pump over a period of 90 minutes. TEMODAR for Injection should be administered only by intravenous infusion. Flush the lines before and after each TEMODAR infusion.

TEMODAR for Injection may be administered in the same intravenous line with 0.9% Sodium Chloride injection only.

Because no data are available on the compatibility of TEMODAR for Injection with other intravenous substances or additives, other medications should not be infused simultaneously through the same intravenous line.

### 3 DOSAGE FORMS AND STRENGTHS

- TEMODAR (temozolomide) Capsules for oral administration
  - 5-mg capsules have opaque white bodies with green caps. The capsule body is imprinted with two stripes, the dosage strength, and the Schering-Plough logo. The cap is imprinted with "TEMODAR."
  - 20-mg capsules have opaque white bodies with yellow caps. The capsule body is imprinted with two stripes, the dosage strength, and the Schering-Plough logo. The cap is imprinted with "TEMODAR."
  - 100-mg capsules have opaque white bodies with pink caps. The capsule body is imprinted with two stripes, the dosage strength, and the Schering-Plough logo. The cap is imprinted with "TEMODAR."
  - 140-mg capsules have opaque white bodies with blue caps. The capsule body is imprinted with two stripes, the dosage strength, and the Schering-Plough logo. The cap is imprinted with "TEMODAR."
  - 180-mg capsules have opaque white bodies with orange caps. The capsule body is imprinted with two stripes, the dosage strength, and the Schering-Plough logo. The cap is imprinted with "TEMODAR."
  - 250-mg capsules have opaque white bodies with white caps. The capsule body is imprinted with two stripes, the dosage strength, and the Schering-Plough logo. The cap is imprinted with "TEMODAR."
- TEMODAR (temozolomide) is available as 100-mg/vial powder for injection. The lyophilized powder is white to light tan/light pink.

### 4 CONTRAINDICATIONS

#### 4.1 Hypersensitivity

TEMODAR (temozolomide) is contraindicated in patients who have a history of hypersensitivity reaction (such as urticaria, allergic reaction including anaphylaxis, toxic epidermal necrolysis, and Stevens-Johnson syndrome) to any of its components. TEMODAR is also contraindicated in patients who have a history of hypersensitivity to dacarbazine (DTIC), since both drugs are metabolized to 5-(3-methyltriazene-1-yl)-imidazole-4-carboxamide (MTIC).

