## 10.0 DESIGN

### 10.1 Description

This will be an open label, uncontrolled Phase 1b/2 trial in patients with newly diagnosed GBM who have recovered from complete or partial surgical resection. All patients will be treated with PLX3397 in addition to standard-of-care combination radiation therapy (RT) plus temozolomide (TMZ) followed by adjuvant TMZ. During Phase 1b dose escalation, two PLX3397 administration schedules, 7 days/week vs. 5 days/week (M-F) will be explored. During Phase 2, patients will be treated with the RP2D.

There are 4 sequential periods: 1-week PLX3397 monotherapy; 6-week PLX3397/RT/TMZ combination therapy; 4-week recovery; and, PLX3397/TMZ adjuvant therapy. PLX3397 will be administered twice daily either 7 days/week or 5 days/week (Monday through Friday) starting 1 week prior to the initiation of RT and will continue twice daily either 7 days/week or 5 days/week (Monday through Friday) during the 6-week course of RT.

Phase 1b PLX3397 dose and schedule cohorts are shown in [Table 2](#).

A detailed Trial Flow Chart is available in [Section 6.0](#), and procedures by study day are provided in [Section 13.0](#).

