### 11.2 Exclusion Criteria

1. Evidence of recurrent GBM or metastases detected outside of the cranial vault.
2. Investigational drug use within 28 days of the first dose of PLX3397 or concurrently.
3. Prior use of Gliadel wafers or any other intratumoral or intracavitary treatment.
4. Prior radiation or chemotherapy for glioblastoma or glioma.
5. Prior chemotherapy or radiosensitizers for cancer of the head and neck (except for T1 glottic cancer) that would result in an overlap of radiation fields.
6. Prior allergic reaction to temozolomide.
7. History of Grade 2 (CTCAE v4) or greater acute intracranial hemorrhage.
8. Active cancer (either concurrent or within the last 3 years) that requires non-surgical therapy (e.g. chemotherapy or radiation therapy), with the exception of surgically treated basal or squamous cell carcinoma of the skin, melanoma in-situ, or carcinoma in-situ of the cervix.
9. Chronic active hepatitis B or C.
10. Refractory nausea and vomiting, malabsorption, biliary shunt, or significant bowel resection that would preclude adequate absorption of study drug.
11. Patients with serious illnesses, uncontrolled infection, medical conditions, or other medical history including abnormal laboratory results, which in the investigator's opinion would be likely to interfere with a patient's participation in the study, or with the interpretation of the results.

12. Women of child-bearing potential who are pregnant or breast feeding.
13. At Screening QTcF  $\geq 450$  msec for males and  $\geq 470$  msec for females.

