### 16.3.8 Contraindications

Temozolomide is contraindicated in patients who have a history of a hypersensitivity reaction to any of its components or to DTIC.

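### Exclusion 6 is narrower than the protocol's own temozolomide contraindication, so the explicit entry criteria do not screen for hypersensitivity to dacarbazine (DTIC) or to a capsule component

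*Combined protocol and SAP*

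**What the plan says.** Temozolomide is not optional. Section 10.1 states: "All patients will be treated with PLX3397 in addition to standard-of-care combination radiation therapy (RT) plus temozolomide (TMZ) followed by adjuvant TMZ".

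The one entry criterion on tolerance of it is exclusion 6, worded alike in the synopsis and in Section 11.2: "Prior allergic reaction to temozolomide".

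The contraindication appears in three other places, each wider than that:

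- Section 16.3.8: "Temozolomide is contraindicated in patients who have a history of a hypersensitivity reaction to any of its components or to DTIC".
- Attachment 4, label highlights: "Known hypersensitivity to any TEMODAR component or to dacarbazine (DTIC".
- Attachment 4, label Section 4.1: "TEMODAR is also contraindicated in patients who have a history of hypersensitivity to dacarbazine (DTIC". The reason given is that both drugs are converted to the same metabolite, MTIC.

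Three other exclusions touch on earlier drug treatment. Exclusion 4 bars "Prior radiation or chemotherapy for glioblastoma or glioma". Exclusion 5 bars "Prior chemotherapy or radiosensitizers for cancer of the head and neck" where radiation fields would overlap. Exclusion 8 bars "Active cancer (either concurrent or within the last 3 years) that requires non-surgical therapy", with listed exceptions. Exclusion 11 lets the investigator exclude on medical history that would probably interfere with participation or interpretation.

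**The concern.** Eligibility is the point at which a known bar to a mandatory treatment should be found. Here the criterion covers a smaller set of histories than the contraindication stated elsewhere in the same protocol.

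Timing adds to this. PLX3397 starts on Cycle 1 Day 1 (Section 13.2) and temozolomide starts with radiotherapy on Cycle 1 Day 8 (Section 13.3). If the history surfaces only when temozolomide is about to be given, the patient has already had about a week of investigational drug and cannot receive the combination under study without departing from Section 16.3.8. If it never surfaces, the patient receives a drug that the protocol lists as contraindicated for that patient.

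**Working it through.** The plan states no figure here that could be reproduced. The check is a comparison of the text, followed by one piece of arithmetic for scale.

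**1. Histories covered**

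| History | Exclusion 6 | Section 16.3.8 and label |
|---|---|---|
| Allergic reaction to temozolomide | named | covered |
| Hypersensitivity to another component of the product | not named | covered |
| Hypersensitivity to DTIC | not named | covered |

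The second row matters in its own right. Label Section 11 lists inactive ingredients, among them lactose, tartaric acid and a gelatin shell. A patient could have reacted to one of these without ever taking temozolomide or DTIC.

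**2. Does another explicit criterion close the gap?**

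- Exclusion 4 reaches only treatment given for glioblastoma or glioma.
- Exclusion 5 reaches only head and neck cancer with overlapping fields.
- Exclusion 8 reaches back three years, so DTIC given earlier for another disease passes.
- No inclusion criterion mentions drug hypersensitivity.
- Exclusion 11 could apply, but it depends on the investigator's judgement and names neither hypersensitivity nor DTIC.

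**3. Does a scheduled procedure prompt the question?** Screening (Section 13.1) includes medical history and concomitant medications, without a specific item on this. The Day 8 list (Section 13.3) starts temozolomide without a contraindication check.

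**4. Where would such a patient fall in the analysis if temozolomide were withheld?**

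- Modified ITT (Section 21.3) requires one dose of study drug and some follow-up, so the patient is included.
- Per protocol (Section 21.3) requires that the entry criteria are met, with four weeks of study drug and 90% of radiotherapy. It sets no temozolomide requirement, so the patient is not removed on that ground.
- For the Phase 1b DLT evaluation, Section 21.1.1 replaces patients found ineligible, and this patient is eligible as the criteria are written. It also replaces patients judged non-evaluable for reasons unrelated to study drug. That could apply, but the term is not defined for missed temozolomide. Section 13.15 adds a discretionary route to replacement.

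**5. Scale.** Section 21.2 combines about 37 Phase 2 patients with 7 from Phase 1b: 37 + 7 = 44. One patient is 1/44 = 2.3% of that set. This is the weight of a single patient and not an expected frequency, because the documents give no rate for DTIC exposure or hypersensitivity.

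**The case against.** The strongest reply is that nothing here directs anyone to give a contraindicated drug. Section 16.3.8 is operative protocol text, Section 16.3 refers the reader to the full label, and exclusion 11 lets the investigator turn such a patient away using history collected before any dosing. An affected patient would need a hypersensitivity to DTIC or to a component and a team that overlooked Section 16.3.8. On the DTIC route the patient would also need past exposure outside the reach of exclusions 4, 5 and 8. Most of this stands. It makes the case rare and the priority low. It does not make the explicit criterion match the contraindication.

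A reader might infer four stronger things that the documents do not support:

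- **That the passages contradict each other.** Exclusion 6 omits histories. It does not say that such a patient may receive temozolomide.
- **That a severe reaction is predictable.** The serious reactions listed in label Section 4.1 are examples of a past reaction that makes the drug contraindicated. The DTIC sentence gives only the shared metabolite. Neither states a probability or a severity for what would follow.
- **That a fixed share of a Phase 1b DLT cohort is lost.** Seven patients are accrued to secure six, and the replacement rules in Sections 21.1.1 and 13.15 may apply.
- **That the safety and analysis consequences add up.** For any one patient they are alternatives. The safety risk arises if the history is missed, and the analysis effect arises if it is noticed and temozolomide is withheld.

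**Conclusion.** The point holds as a mismatch in scope: the entry criterion is narrower than the contraindication stated in Section 16.3.8 and in both places in the label. A patient with a history of hypersensitivity to DTIC or to a component can meet every explicit criterion and begin PLX3397 before the conflict comes to light. Detection then rests on a discretionary clause or on someone reading Section 16.3.8.

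The size is small. The frequency is unknown and assumed to be low. Type I error, power and sample size do not change. One such patient would make up 2.3% of a combined set of 44, a weight that the primary analysis can absorb. The conclusion assumes that the eligibility lists in the synopsis and Section 11.2 are the complete criteria, and it has practical value only for patients still to be enrolled. It is a free patient-safety improvement of low priority.

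**What to change.** Reconcile exclusion 6, in both the synopsis and Section 11.2, with Section 16.3.8 and the two label statements in Attachment 4, so that the entry criterion and the stated contraindications cover the same histories. The clinical content of the reconciled rule is for the sponsor and investigators to settle.

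The cost is an edit of about one line in each place, which can be carried in any protocol amendment. It needs no new procedure, because medical history is already taken at Screening, and the effect on accrual should be negligible. The statistical sections need no change.
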